Participants who prematurely discontinue injectable study product permanently, will continue on-study for an additional 48 weeks after their last study product injection, per the long-term safety and washout PK follow-up (LSFU) schedule.

The sample size for Cohort 2 will be up to 155 adolescents in total. Up to 100 adolescents, who had not previously participated in Cohort 1 (i.e., Cohort 1-naïve), will be enrolled to achieve approximately 70 evaluable. Cohort 2A participants will receive the final recommended oral doses followed by the LA doses of CAB and RPV. Cohort 2B participants will receive the final recommended LA doses of CAB and RPV. Adolescents who participated in Cohort 1 (i.e., Cohort

1 rollovers; up to 55) may continue study participation in Cohort 2, if eligible, in addition to the up to 100 Cohort 2 participants newly enrolled to the study.

At the Week 96/92 visit, Cohort 2A Step 4 and Cohort 2B Step 5 participants continuing to receive injectable CAB LA + RPV LA external to the protocol will exit the study. Section 14.11 of protocol Version 4.0 has more information regarding post-trial access to study products. Participants who discontinue injectable CAB LA + RPV LA at the Week 96/92 visit will not exit the study. These participants will be followed for 48 weeks per the LSFU visit schedule.

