## 2.4 Overview of Sample Size Considerations

Details of sample size considerations are provided in Section 9.4 of protocol Version 4.0. Briefly, the sample was driven primarily by safety considerations. **Table 1** below presents exact (Clopper-Pearson) 95% confidence intervals (CI) around various potential rates (0% and 20%) of Grade 3 or higher adverse events (AE) which might be observed in a total sample of 70 participants who enrolled directly into Cohort 2A or 2B (i.e., the primary analysis set for the Cohort 2 safety assessment) as well as for 100 participants who might contribute data to the safety analysis (i.e., all those exposed to the final recommended dose for Cohort 2).

**Table 1.** Percent of Participants Experiencing Grade 3 or Higher Adverse Events with Exact (Clopper-Pearson) 95% Confidence Intervals.

N	n (%) with Grade 3 or higher Adverse Events	95% CI
70	0 (0%)	0.00, 0.05
100	0 (0%)	0.00, 0.04
70	14 (20%)	0.11, 0.31
100	20 (20%)	0.13, 0.29

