## **4 Analysis Sets**

The following analysis sets are defined:

**All Treated:** All participants who took at least one dose of any study product in Cohort 2

**Evaluable:** For analysis purposes, evaluable participants will be defined as having been treated exclusively on the final recommended dose and either (1) having completed all treatment regimen through Week 24 (Cohort 2A)/Week 20 (Cohort 2B) or (2) having experienced any of the following:

- death that is attributable to the study product(s), OR
- study product-related Grade 3 or higher event (excluding injection-site AEs), OR
- permanently discontinued from treatment due to study product-related toxicities (regardless of grade) during these weeks of treatment.

Notes:

- An additional requirement for inclusion in the primary analyses for Cohort 2 is that the participants must be directly accrued to this cohort and be exclusively treated with the combination of the two study products; this will be approximately 70 participants.

- Oral bridging in Cohort 2 will not be counted as a substitute for an injection but as long as the recommended number of injections were given through Week 24/Week 20, even if they were out of window, the participant will be considered evaluable.

**Cohort 1 Rollover:** Cohort 2 participants who were previously enrolled to Cohort 1.

**Cohort 1-Naïve:** Cohort 2 participants who were enrolled directly to Cohort 2 without prior participation in Cohort 1.

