## 5 General Considerations

The derivation of PK parameters will be performed by the IMPAACT 2017 protocol pharmacologists, as described in the PK SAP. The statistical summaries to be prepared by the statisticians are described in this Primary SAP.

Continuous variables will be summarized by N, N missing, mean, standard deviation, and quantiles of minimum, 25th percentile, median, 75th percentile, and maximum. Categorical variables will be summarized by N (%) in each category, excluding the missing category in the denominator.

For all baseline demographics and exposure analyses, results will be presented for the All Treated analysis set. The baseline value will be the latest pre-dose assessment with a non-missing value, including those from unscheduled visits. If time is not collected, Day 1 assessments are assumed to be taken prior to first dose and used as baseline. Unless otherwise stated, if baseline data are missing, no derivation will be performed and baseline will be set to missing.

All safety data will be considered from the first patient exposure to study treatment. Each participant's safety data will be summarized as: (1) the worst grade of each AE and (2) the worst grade of each AE judged to be related to study treatment.

Listings of all Grade 3 or higher AEs regardless of treatment attribution, serious AEs meeting ICH criteria assessed as related to study product(s), and AEs which resulted in permanent discontinuation of study product(s) or death will be provided. These categories of AEs will also be summarized and broken down by System Organ Class. The Division of AIDS Table for Grading the Severity of Adult and Pediatric Adverse Events (DAIDS AE Grading Table), Corrected Version 2.1, dated July 2017, will be used in this study. This table is available on the RSC website at <https://rsc.niaid.nih.gov/clinical-research-sites/daids-adverse-event-grading-tables>.

Analyses of primary and secondary outcome measures will include Cohort 1-naïve evaluable participants, as defined above. Supplementary analyses of safety and virologic outcome measures will include all participants (Cohort 1-naïve and Cohort 1 rollovers) who received study products (All Treated analysis set referenced above).

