Occurrence of each of the following through 24 weeks (for oral lead-in) or 20 weeks (for direct to injection):  
 
• Any adverse event
 
• Severe, potentially life-threatening, or death event
 
• Severe, potentially life-threatening, or death event assessed as related to CAB and/or RPV
 
• Serious adverse event related to CAB and/or RPV
 
• Permanent discontinuation of CAB and/or RPV due to adverse event assessed as related to CAB and/or RPV
 
• Death due to adverse event assessed as related to CAB and/or RPV
 
	Occurrence of each of the following through Week 24 (Cohort 2A)/through Week 20 (Cohort 2B):  
 
• Any adverse event, regardless of grade
 
• Grade 3 or higher adverse event
 
• Grade 3 or higher adverse event assessed as related to study product(s)
 
• Serious adverse event meeting ICH criteria assessed as related to study product(s)
 
• Permanent discontinuation of study product due to adverse event assessed as related to study product(s)
 
• Death due to adverse event assessed as related to study product(s)
 

Handling of intercurrent events	Handling of missing data
The following intercurrent events are relevant to the estimand:  
 
1. Discontinuation of CAB and/or RPV due to toxicity
 
2. Death related to CAB and/or RPV
 
 
These intercurrent events (1, 2) will be addressed using a while on treatment strategy.
 
 
3. Discontinuation of CAB and/or RPV due to non-toxicity reasons
 
4. Death unrelated to CAB and/or RPV
 
 
These intercurrent events (3, 4) will be addressed using a principal stratum approach.
	Missing data will be addressed using a “complete case” approach, defined per outcome measure.
Population-level summary measure	Analysis approach
Probability of having at least one event (any adverse event; severe, potentially life-threatening, or death event; severe, potentially	Proportion of participants with at least one event (any adverse event; Grade 3 or higher adverse event; Grade 3 or higher

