### Sensitivity Analyses

Because complete case approach assumes data are missing completely at random, we will use multiple imputation that assumes missing at random as a sensitivity analysis. We will create 100 imputed data sets using appropriate fully conditional specified (FCS) model and combine results using Rubin's rules. We will also present estimates assuming "best case" (i.e., probability of event = 0) and "worst case" (i.e., probability of event = 1) scenarios. Of note, only participants who are deemed evaluable will be included in this primary analysis; therefore, very little (if any) missing data is expected. Sensitivity analyses related to missing data in the All Treated analysis set will be addressed in the supplementary analyses.

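### The primary safety set is selected on post-baseline related events that are themselves primary outcomes, and no analysis of all treated Cohort 1-naïve participants shows what that selection does

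*SAP*

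**What the plan says.** SAP Section 4 gives two routes into the Evaluable set. The first is completion: "having completed all treatment regimen through Week 24 (Cohort 2A)/Week 20 (Cohort 2B"). The second is one of three events: an attributable death; an event under the item "study product-related Grade 3 or higher event (excluding injection-site AEs), OR"; or permanent discontinuation for related toxicity of any grade. Treatment must also have been exclusively at the final recommended dose. Section 5 restricts primary and secondary outcomes to Cohort 1-naïve evaluable participants.

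Section 3.1 lists six primary outcomes: any AE; Grade 3 or higher AE whatever its cause; related Grade 3 or higher AE; related serious AE; discontinuation for a related AE; and related death. The outcome definitions do not exclude injection-site events.

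Section 6.1 assigns discontinuation due to toxicity and related death to a while-on-treatment strategy. For non-toxicity discontinuation and unrelated death, "These intercurrent events (3, 4) will be addressed using a principal stratum approach". Its sensitivity analyses stay inside the set: "only participants who are deemed evaluable will be included in this primary analysis; therefore, very little (if any) missing data is expected".

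The wider analysis is described in Section 5: "Supplementary analyses of safety and virologic outcome measures will include all participants (Cohort 1-naïve and Cohort 1 rollovers) who received study products".

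On numbers, Section 2.1 says "The sample size for Cohort 2 will be up to 155 adolescents in total" and "Up to 100 adolescents, who had not previously participated in Cohort 1 (i.e., Cohort 1-naïve), will be enrolled to achieve approximately 70 evaluable". Section 2.4 describes the N = 100 rows of Table 1 as "100 participants who might contribute data to the safety analysis (i.e., all those exposed to the final recommended dose for Cohort 2").

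**The concern.** Take two participants who stop early for the same non-toxicity reason. The one who has had a related, non-injection-site Grade 3 event is counted in numerator and denominator. The event-free one is counted in neither. Membership of the safety set therefore depends on the outcome being estimated.

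The opposite can happen with all-cause events. Three kinds of participant are left out of the Grade 3 or higher proportions unless they also had a qualifying event:

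- a participant who dies of an unrelated cause;
- a participant who leaves after an unrelated Grade 3 AE;
- a participant with a related Grade 3 injection-site AE who leaves for a non-toxicity reason.

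Safety is the primary objective, so these are the trial's headline proportions. A reader will want to know how far they move when everyone who was dosed is counted. The planned analyses do not answer that for the newly enrolled adolescents.

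**Working it through.** **1. The plan's own figures.** Exact two-sided 95% Clopper-Pearson limits are the 2.5% quantile of Beta(x, n−x+1) and the 97.5% quantile of Beta(x+1, n−x).

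| x/n | Computed | Table 1 |
|---|---|---|
| 0/70 | 0 to 0.051 | 0.00, 0.05 |
| 0/100 | 0 to 0.036 | 0.00, 0.04 |
| 14/70 | 0.114 to 0.313 | 0.11, 0.31 |
| 20/100 | 0.127 to 0.292 | 0.13, 0.29 |

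All four reproduce.

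**2. Outcomes that are also entry routes.** Let T be the number of treated Cohort 1-naïve participants, of whom 70 are evaluable. Assume that those left out are non-completers on the final dose. None of them can have had a related death, a related discontinuation or a related non-injection-site Grade 3 or higher event, because each of these would have admitted them. With x such events the plan reports x/70 where the all-treated figure is x/T, a ratio of T/70. The SAP does not state T beyond a ceiling of 100, so T = 75 to 100 is my assumed range.

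| T | T/70 | x = 5 | x = 14 |
|---|---|---|---|
| 70 (Evaluable) | 1.00 | 7.1% (2.4 to 15.9) | 20.0% (11.4 to 31.3) |
| 75 | 1.07 | 6.7% (2.2 to 14.9) | 18.7% (10.6 to 29.3) |
| 100 | 1.43 | 5.0% (1.6 to 11.3) | 14.0% (7.9 to 22.4) |

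**3. All-cause Grade 3 or higher.** Let k of the T − 70 participants left out have such an event. The all-treated proportion is (14 + k)/T. At T = 100:

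- k = 0 gives 14%;
- k = 6 gives 20%, equal to 14/70;
- k = 9 gives 23% (15.2 to 32.5);
- k = 30, the arithmetic extreme, gives 44% (34.1 to 54.3).

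The Evaluable figure understates only if more than 20% of those left out had an event.

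**4. How direction depends on leaving.** I ran a simulation with assumptions that are mine, not the SAP's: 3% related and 12% unrelated Grade 3 or higher risk over the period, 25% non-toxicity dropout, exponential times, and no injection-site events. Full-period all-cause risk is 1 − 0.97 × 0.88 = 14.6%.

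| Unrelated Grade 3+ cases who leave | Evaluable | All treated |
|---|---|---|
| 0% | 15.0% | 12.8% |
| 10% | 14.1% | 12.8% |
| 25% | 12.5% | 12.8% |
| 50% | 9.7% | 12.8% |

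For related events, Evaluable gives about 3.5% and all treated about 2.6%, against 3.0%.

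**5. Why the pooled analysis does not isolate selection.** Rollovers may be 55/155 = 35% of All Treated. If naïve participants had 20% and rollovers 10% (assumed), the pool shows (100 × 0.20 + 55 × 0.10)/155 = 16.5%. A gap between that and the Evaluable figure could come from selection, from prior exposure to one product, or from both.

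**6. Strategy against set.** Section 6.1 covers discontinuation due to toxicity, with no requirement that the toxicity be related. Section 4 and the analysis-set cell of Section 6.1 admit only related toxicity. A participant who stops for an unrelated AE therefore has a while-on-treatment strategy but, without another qualifying event, is not in the set to which it applies.

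**7. Table 1 label.** The N = 100 rows are described as everyone exposed in Cohort 2. By Section 2.1 that is up to 100 + 55 = 155. The figure 100 matches the Cohort 1-naïve ceiling, a set for which no proportion is planned.

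**The case against.** The strongest defence is that nothing is concealed and that the alternative set is also imperfect. Section 5 requires listings of every Grade 3 or higher AE regardless of attribution, and of AEs leading to discontinuation or death; none of these is restricted to Evaluable. The supplementary analysis in Section 6.1 includes every leaver, with imputation and best/worst-case estimates. The study is non-comparative, and the SAP sets no threshold on these proportions. An all-treated proportion counts early leavers as event-free after they leave; in step 4 it misses the full-period risk by about as much as Evaluable does for related events, in the opposite direction. All of this stands. It argues against replacing the primary set, but not against showing the missing comparison.

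Some stronger inferences are tempting, and the document does not support them:

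- **Every leaver with a related Grade 3 event is kept.** Injection-site AEs do not confer evaluability, so bias in the overall related Grade 3 or higher outcome can also run either way.
- **All-cause events are necessarily understated.** Steps 3 and 4 show that the sign depends on who leaves.
- **Thirty per cent will be dropped.** The figures of up to 100 and approximately 70 are a planning ceiling and a target, not a predicted loss.
- **The best/worst-case analyses are empty.** That is nearly so inside the Evaluable set, as the SAP discloses, but they are also run in All Treated.

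One could read toxicity in Section 6.1 as meaning related toxicity. Stopping for an unrelated AE would then fall under the non-toxicity event, but the text does not say so.

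**Conclusion.** The point holds as a gap in the safety analysis. Selection into the primary set depends on primary outcomes. Relative to all treated Cohort 1-naïve participants, proportions for related death, related discontinuation and related non-injection-site Grade 3 or higher events are inflated by 1.07 to 1.43 for 75 to 100 treated and 70 evaluable. This assumes that exclusions are for non-completion rather than dose. For all-cause Grade 3 or higher events the direction is unknown in advance.

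The inflation is measured against the all-treated proportion, which is not itself the full-period risk. The wider analysis exists but cannot attribute a difference to selection, because it adds rollovers at the same time. The toxicity wording and the Table 1 label are smaller inconsistencies; the Table 1 intervals themselves are correct.

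**What to change.** - Report all six primary safety outcomes for All Treated Cohort 1-naïve participants alongside the Evaluable result, with exact CIs and the existing best/worst-case analyses. Do the same for the Week 48/44 outcomes in Section 6.2.1.
- Present All Treated split by Cohort 1 history before pooling.
- Reconcile the first intercurrent event in Section 6.1 (and its copy in Section 6.2.1) with the related-only rule in the Evaluable definition.
- Relabel the N = 100 rows of Table 1 as all treated Cohort 1-naïve. If the pooled set is wanted, add rows for up to 155: 0/155 has an upper limit of 2.4%, and 31/155 = 20% has a CI of 14.0 to 27.2%.

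The cost is SAP wording and reruns of the same programs, since Section 4 already defines All Treated and Cohort 1-Naïve. The downside is that early leavers contribute shorter follow-up, which can dilute all-treated proportions. They should be shown with exposure time.

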### Sensitivity Analyses

Because complete case approach assumes data are missing completely at random, we will use multiple imputation that assumes missing at random as a sensitivity analysis. We will create 100 imputed data sets using appropriate fully conditional specified (FCS) model and combine results using Rubin's rules. We will also present estimates assuming "best case" (i.e., probability of event = 0) and "worst case" (i.e., probability of event = 1) scenarios. Of note, only participants who are deemed evaluable will be included in this primary analysis; therefore, very little (if any) missing data is expected. Sensitivity analyses related to missing data in the All Treated analysis set will be addressed in the supplementary analyses.

### Supplementary Analyses

Supplementary analyses for the primary outcome measures will include all participants (Cohort 1-naïve and Cohort 1 rollovers) who received study products. All intercurrent events will be addressed using a while on treatment strategy, and missing data will be handled using a complete case approach. Because this approach assumes data are missing completely at random, we will use multiple imputation that assumes missing at random as a sensitivity analysis. We will create 100 imputed data sets using appropriate FCS model and combine results using Rubin's rules. We will also present estimates assuming "best case" (i.e., probability of event = 0) and "worst case" (i.e., probability of event = 1) scenarios.

## **6.2 Secondary Estimands and Analysis**

### **6.2.1 Safety Estimands**

**Secondary Objective 1:** To assess the safety of CAB + RPV in adolescents living with HIV who are virologically suppressed through Week 48 (Cohort 2A)/Week 44 (Cohort 2B).

Estimand	Probability of a virologically suppressed adolescent (aged 12 to <18 years) living with HIV-1, who was either exclusively treated with the combination of RPV and CAB at the final recommended dose for 48 weeks (for oral lead-in) or 44 weeks (for direct to injection), experienced a severe, potentially life-threatening, or death event attributable to CAB and/or RPV, or permanently
----------	--

	discontinued CAB and/or RPV due to a related toxicity, having at least one event (any adverse event; severe, potentially life-threatening, or death event; severe, potentially life-threatening, or death event assessed as related to CAB and/or RPV; serious adverse event assessed as related to CAB and/or RPV; permanent discontinuation of CAB and/or RPV due to adverse event assessed as related to CAB and/or RPV; death due to adverse event assessed as related to CAB and/or RPV).
Treatment	30 mg CAB + 25 mg RPV once daily orally for four weeks followed by IM injections of 600 mg CAB LA + 900 mg RPV LA (first and second injections four weeks apart with subsequent injections every eight weeks) or direct to IM injections of 600 mg CAB LA + 900 mg RPV LA (first and second injections four weeks apart with subsequent injections every eight weeks).
Target population	Analysis set
Virologically suppressed children and adolescents 12 to <18 years of age living with HIV-1 exclusively treated with the combination of RPV and CAB at the final recommended dose for either 48 weeks (for oral lead-in) or 44 weeks (for direct to injection).	
Participants who are exclusively treated with the combination of RPV and CAB at the final recommended dose and either completed all treatment regimen through the Week 48 (Cohort 2A)/Week 44 (Cohort 2B) visit or experienced any of the following:
 
 
• death that is attributable to the study product(s), OR
 
• study product-related Grade 3 or higher adverse event (excluding injection-site AEs), OR
 
• permanent discontinuation from treatment due to study product-related toxicities (regardless of grade) during these weeks of treatment.
 

Variable(s)	Outcome measure(s)
Occurrence of each of the following through 48 weeks (for oral lead-in) or 44 weeks (for direct to injection): 
 
• Any adverse event
 
• Severe, potentially life-threatening, or death event
 
• Severe, potentially life-threatening, or death event assessed as related to CAB and/or RPV
 
	Occurrence of each of the following through Week 48 (Cohort 2A)/through Week 44 (Cohort 2B): 
 
• Any adverse event, regardless of grade
 
• Grade 3 or higher adverse event
 
• Grade 3 or higher adverse event assessed as related to study product(s)
 

 
• Serious adverse event related to CAB and/or RPV
 
• Permanent discontinuation of CAB and/or RPV due to adverse event assessed as related to CAB and/or RPV
 
• Death due to adverse event assessed as related to CAB and/or RPV
 
	
 
• Serious adverse event meeting ICH criteria assessed as related to study product(s)
 
• Permanent discontinuation of study product due to adverse event assessed as related to study product(s)
 
• Death due to adverse event assessed as related to study product(s)
 

Handling of intercurrent events	Handling of missing data

The following intercurrent events are relevant to the estimand:
 
 
1. Discontinuation of CAB and/or RPV due to toxicity
 
2. Death related to CAB and/or RPV
 
 
These intercurrent events (1, 2) will be addressed using a while on treatment strategy.
 
 
3. Discontinuation of CAB and/or RPV due to non-toxicity reasons
 
4. Death unrelated to CAB and/or RPV
 
 
These intercurrent events (3, 4) will be addressed using a principal stratum approach.
	Missing data will be addressed using a “complete case” approach, defined per outcome measure.
Population-level summary measure	Analysis approach
Probability of having at least one event (any adverse event; severe, potentially life-threatening, or death event; severe, potentially life-threatening, or death event assessed as related to CAB and/or RPV; serious adverse event assessed as related to CAB and/or RPV; permanent discontinuation of CAB and/or RPV due to adverse event assessed as related to CAB and/or RPV; death due to adverse event assessed as related to CAB and/or RPV) through 48 weeks (for oral lead-in) or 44 weeks (for direct to injection).	Proportion of participants with at least one event (any adverse event; Grade 3 or higher adverse event; Grade 3 or higher adverse event assessed as related to study product(s); serious adverse event meeting ICH criteria assessed as related to study product(s); permanent discontinuation of study product due to adverse event assessed as related to study product(s); death due to adverse event assessed as related to study product(s)) through Week 48 (Cohort 2A)/through Week 44 (Cohort 2B), bounded by an exact (Clopper-Pearson) 95% CI.

